## 7. Research Plan:

The study is a randomized, open-label, comparative effectiveness clinical trial in 180 total patients with GERD or dyspepsia symptoms who will be randomized to either conventional or genotype-supported treatment of GERD and dyspepsia. A total of 120 patients will be enrolled in the UF Health Gastroenterology Clinics in Gainesville, and 60 will be enrolled in a parallel study (under separate IRB protocol) at Nemours Children's Hospital Gastroenterology Clinics in Orlando, FL. Each site will be responsible for overseeing patient care and research at their respective facility. All participants will have symptoms of GERD or related diseases and be candidates for PPI therapy or on PPI therapy with continued symptoms.

We will enroll a total of 180 patients between the UF Health and Nemours sites, which should allow for sufficient power to detect our efficacy endpoint (see power calculation below). We will also collect data from the health records for up to 24 months after enrollment on upper respiratory infection (cold), sore throat, strep throat, bronchitis, pneumonia, ear infection, acute sinusitis (sinus infection), bone fractures, renal function, and gastrointestinal infections for preliminary assessment of the effects of *CYP2C19*-supported PPI dosing on adverse effects. This exploratory arm will provide data to inform power calculations for a larger study focused on preventing PPI-associated adverse events through genotype-supported dosing.

**Inclusion Criteria.** A total of 120 patients with GERD or related symptoms will be enrolled at UF Health. An additional 60 patients will be enrolled at Nemours Children's Hospital Gastroenterology Clinics under a separate IRB protocol. For this protocol, any patient over the age of 17 who presents to GI clinic with GERD or related symptoms and is either 1) being initiated on PPI therapy or 2) continues to have symptoms despite PPI therapy will be considered eligible for the study.

Exclusion Criteria. This study will exclude patients who have had extensive esophageal or gastric surgery or any major chronic illness or condition that in the opinion of the gastroenterologist that would interfere with participation in the study.

Participant Recruitment Methods.

Prior to enrolling their patients, clinicians at participating GI clinics (investigators for this study) will be asked to complete surveys that assess their knowledge, attitudes, and beliefs as they relate to pharmacogenetics testing.

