Genotyping and result reporting. Genotyping will be done by the CLIA-licensed UF Pathology Laboratory, as has been done for over 1,600 patients in the UF Health CYP2C19-clopidogrel implementation, with genotype results reported in the EHR. For patients randomized to the genotype-supported arm, genotype results will be available in approximately 2 weeks. For patients randomized to the conventional treatment arm, the genotype results will be resulted in the EHR after the patient completes study participation (12 weeks after patient enrollment). The patient's clinician will be educated about the genotype results and their implication for PPI response. A recommendation for a dose increase will be provided for RMs and UMs (approximately 30% to 35% of patients). For patients with other genotypes, clinicians will be advised that usual PPI doses are expected to be effective that lower doses may be sufficient for symptoms management in PMs. Clinicians will also be provided quick reference guides that will include phenotype, genotype, dosing recommendations, and educational information. The PMP Committee has convened with the GI clinicians to evaluate and approve the dosing recommendations for adults based on CYP2C19 genotype. Clinical decision support tools in the EMR will also be implemented that will provide this guidance to the treating clinician. While dosing recommendations will be provided based on genotype results, the ultimate prescribing decision will be left to the discretion of the treating physician.

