Assessment of PPI efficacy and adverse effects. Our primary outcome will be the effectiveness of PPI therapy, which will be determined via two questionnaires: RDQ and GOS scale, administered by study personnel at baseline and 12 weeks. The RDQ was developed to monitor treatment response over time and evaluates 6 symptoms (12 items) covering 3 domains: heartburn, regurgitation, and upper abdominal pain. Each symptom is evaluated using a 6-point Likert scale to assess frequency and severity over the previous week. Each symptom is rated from 1 (did not have) to 6 (severe), and the RDQ mean score is calculated as the mean response to the 12 items. The RDQ mean score thus ranges from 1 to 6 and has been psychometrically validated. The GOS scale evaluates 18 symptoms, with each rated from 1 (no problem) to 7 (very severe). Similar to the RDQ, the mean score is calculated as the mean response to the 18 items, with mean scores ranging from 1 to 7. Patient participation will end after they complete the approximate 12 week questionnaire. However, we will continue to

follow patients over 24 months through medical record review to assess adverse outcomes for occurrence of upper respiratory infection (cold), sore throat, strep throat, bronchitis, pneumonia, ear infection, acute sinusitis (sinus infection), bone fractures, renal function and gastrointestinal infections.

Metrics for assessing success of pharmacogenetic testing in clinical practice. We will test a variety of variables that will provide insight into attitudes and acceptability of pharmacogenetic testing. These will include: 1) percent of patients approached about the study who agree to participate; 2) surveys of patients and clinic staff on knowledge, attitudes, and beliefs about pharmacogenetic testing; and 3) the percent of the time a dosing recommendation for a patient in the genotype-supported arm is accepted by the clinician. Patients will be surveyed about knowledge, attitudes, and beliefs about pharmacogenetic testing using questionnaires on enrollment and at the end of their study participation. Clinic staff will be surveyed about knowledge, attitudes, and beliefs about testing at the beginning and end of the study.

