With 180 total patients (90 patients in each arm), we expect approximately 30 patients in each arm to have the genotype of interest (i.e. RM or UM). At alpha of 0.05, we will have 80% power to detect effect size of  $\geq 0.74$  in the RDQ score in RMs/UMs. This effect size is equivalent to a RDQ score difference of 1.22 for regurgitation and a score difference of 0.93 for heart burn. These differences in RDQ scores are smaller than what is considered clinically significant. Therefore our study is well-powered.

In summary, by studying a total 180 patients (120 from UF Health and 60 from Nemours), the data suggest we will have excellent power to detect an efficacy endpoint. Data generated from this protocol on adverse effects will also help us define the incidence of the adverse effect phenotypes to inform sample size for a future pragmatic trial examining effects of genotype-supported dosing on PPI safety endpoints.

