These data support the hypothesis that genotype-guided dosing of PPIs would reduce treatment failures in RMs and UMs and minimize PPI-associated infections (and perhaps other adverse effects) in IMs and PMs. The overarching goals of this project are to use longitudinal, electronic health record (EHR) data to add to the body of evidence on PPI efficacy and safety by CYP2C19 genotype, and to document the feasibility and potential clinical benefits of CYP2C19 genotype-supported PPI dosing.

**Aim1:** Define clinical outcomes in PPI-treated patients based on CYP2C19 genotype. This aim will be conducted as a cross-network project with Vanderbilt, the other IGNITE site with substantial CYP2C19 genotype data in the EHR. Between the two institutions, we have CYP2C19 genotype data in the EHR on more than 16,000 patients, of whom more than 10,000 have exposure to a PPI. This provides significant power to test the influence of genotype on clinical outcomes with PPI use. The hypothesis is that PMs and IMs will have better control of GERD, but increased rates of adverse events (infection, bone fractures, adverse effects on kidney). In contrast, rapid metabolizers (RM and UMs) are more likely to develop refractory GERD and lower rates of PPI-related complications.

**Aim 2:** Implement pharmacogenetic testing of the CYP2C19 gene-PPI drug pair in adults at UF Health and in children at Nemours Children's Health System in the context of a comparative effectiveness genotype-supported vs. conventional PPI dosing trial. Given that PPI efficacy and adverse events are related to PPI exposure and to metabolizer phenotype, individualizing treatment using CYP2C19 genotype guided dosing is expected to improve patient outcomes. We hypothesize that genotype-guided PPI dosing will reduce the rates of infection, fracture, adverse kidney outcomes and evoke equivalent efficacy for GERD symptoms compared to conventional dosing in children and adults referred to Nemours Children's Hospital and UF Health. We will evaluate physician acceptance of genetic information into clinical practice and potential impact on clinical outcomes.

**Aim3.** Using genotype and phenotype data in the EHR, conduct a genome-wide association study (PheWAS) on CYP2C19 genotype-inferred phenotype. We will conduct this aim in collaboration with Vanderbilt University, who will lead the aim. Please see their proposal for specific details.

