#### **STUDY DESIGN\_ Focus on Aim2 for Nemours Children's Hospital**

**Aim 2: Implement pharmacogenetic testing of the CYP2C19 gene-PPI drug pair in adults at UF Health and in children at Nemours Children's Hospital in the context of a comparative effectiveness genotype-supported vs. conventional PPI dosing trial.**

Overview. We have designed a comparative effectiveness clinical trial testing conventional PPI dosing with genotype-supported dosing with clinically meaningful outcomes to determine the feasibility of genetic testing in a pediatric and adult setting. The primary outcome is a composite end point of upper respiratory infections pneumonia, acute gastroenteritis, adverse kidney effects and bone fractures.

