Study Design. The study is a randomized, open-label, comparative effectiveness clinical trial in 180 patients (60 children, 120 adults) with GERD or any stomach acid mediated condition that will require a PPI. Patients will volunteer to be randomized to either conventional PPI treatment or genotype-supported PPI treatment. All participants will have symptoms of GERD or related diseases who are candidates for PPI therapy or who are on PPI therapy and classified as refractory GERD. Adult patients will be enrolled at UF Health Gastroenterology Clinics and children will be enrolled at the Nemours Children's Hospital Gastroenterology Clinics. After obtaining informed consent, participants will be genotyped and randomly assigned to either conventional treatment or genotype-supported PPI therapy using a randomization table. At NCH, study participants in the control/conventional arm will be blinded on CYP2C19 metabolizer status. Study staff members will not be blinded to any study procedures or determinations as this will improve and facilitate study feasibility. At the end of study period (i.e. 8-12 weeks) study participants in the control/conventional arm will be revealed of metabolizer phenotype status. We will also collect data from the health records for up to 24 months after enrollment on upper respiratory infection (cold), sore throat, strep throat, bronchitis, pneumonia, ear infection, acute sinusitis (sinus infection), bone fractures, renal function, and gastrointestinal infections for preliminary assessment of the effects of CYP2C19-supported PPI dosing on adverse effects.

Participation stipends. Each participant will receive \$25 dollars at the end of study participation. Participants must have completed all study procedures by the end of the study period in order to receive the complete study stipend. If a study participant decides to withdraw from study before the end of study period (before 3 months), the participant will receive a pro-rated stipend. A deposit will be provided in a single CT Payer master card. Each participant will be provided a CT Payer (master card) at the moment of consent. The CT Payer card will be uploaded with the stipend at the end of study participation. Participants whom insurance coverage is limited, a separate deposit will be provided to cover study therapy expenses. We expect to incur in study drug expenses for participants with higher PPI dose prescriptions than conventional dosing (i.e. RMs and UMs).

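### Adverse-event follow-up runs to 24 months without a split at about week 12, when UF control genotypes are posted; separately, two Nemours primary components are listed as collected only in the preliminary record review

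*Combined protocol and SAP*

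**What the plan says.** **UF protocol.** In Section 7 (Research Plan), the outcome paragraph ends participation at the questionnaire of about 12 weeks, but the team will continue to "follow patients over 24 months through medical record review to assess adverse outcomes". The stated use is planning: "This exploratory arm will provide data to inform power calculations for a larger study focused on preventing PPI-associated adverse events through genotype-supported dosing". The power section adds that the data will help "define the incidence of the adverse effect phenotypes to inform sample size for a future pragmatic trial". On genotype results, the same Section 7 says: "For patients randomized to the conventional treatment arm, the genotype results will be resulted in the EHR after the patient completes study participation", and puts this 12 weeks after enrollment. Results in the genotype-supported arm take about 2 weeks. The clinician education and decision support described next are not limited to one arm.

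**Nemours protocol.** Aim 2 states: "We hypothesize that genotype-guided PPI dosing will reduce the rates of infection, fracture, adverse kidney outcomes". The study design overview states: "The primary outcome is a composite end point of upper respiratory infections pneumonia, acute gastroenteritis, adverse kidney effects and bone fractures". The Study Design paragraph says that at 8-12 weeks "study participants in the control/conventional arm will be revealed of metabolizer phenotype status", and that study staff are not blinded. Its list of items for record review up to 24 months ends with "bone fractures, renal function, and gastrointestinal infections for preliminary assessment of the effects of CYP2C19-supported PPI dosing on adverse effects". The Dosing paragraph gives a treatment period of 8-12 weeks. The genetic results paragraph enters results in the health record and withholds control results from patients and families through the portal. The Statistical analysis section names Kaplan-Meier and Cox methods without a time window.

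**The concern.** The record review is meant to describe what genotype-supported dosing does to adverse events compared with conventional dosing. At UF that contrast is protected only until control results are posted. After that, a control patient's clinician has the same kind of information as a clinician in the other arm, and may or may not use it. The plan treats early access as a problem in another place: Section 7 allows a control patient to be withdrawn if the genetic test is ordered during the study. It does not carry that logic into the longer follow-up.

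Two things are at stake. At UF, a diluted arm difference could be taken as the dosing effect when the next trial is sized, or post-release control incidence could be taken as incidence under conventional care. At Nemours the issue is different and touches a primary hypothesis: two components of the tested composite have no listed source other than a review called preliminary, and the period over which events count is not stated.

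**Working it through.** **1. Follow-up windows at UF** (24 months taken as 104 weeks)
- After control release: (104 - 12)/104 = 92/104 = 88.5%.
- Before control release: 12/104 = 11.5%.
- Results available in one arm only, weeks 2 to 12: 10/104 = 9.6%.

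**2. The plan's own adverse-event power figure.** The Nemours Power calculation gives 80% power, alpha 0.05, 89 patients with loss-of-function alleles per arm and a 29% relative reduction. It gives no control event rate, so it cannot be reproduced directly. Solving for the rate p that gives 80% power, two-sided, with p2 = 0.71p and m the mean of p and p2:

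power = Phi{ [(p - p2)√n - 1.96√(2m(1 - m))] / √(p(1 - p) + p2(1 - p2)) }

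With n = 89, p = 0.704 and p2 = 0.500, this is (1.926 - 1.357)/0.677 = 0.84, so power = 0.80. The implied control rate is about 70%. No period is attached to it, so the figure does not supply the missing horizon.

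**3. Direction of dilution at UF (illustration only).** Assume constant rates, an immediate effect, a true rate ratio of 0.71 lasting all 24 months, and a fraction c of the control arm's excess rate disappearing after week 12. The unsplit ratio is

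(104 × 0.71) / [12 + 92 × (1 - 0.29c)]

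| c | Unsplit 24-month ratio |
|---|---|
| 0 | 73.84/104.00 = 0.71 |
| 0.5 | 73.84/90.66 = 0.81 |
| 1 | 73.84/77.32 = 0.96 |

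Cut at week 12, the ratio is 0.71 in every row. The documents give neither c nor the true ratio.

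**4. Events before week 12 at UF** (120 adults, 60 per arm; the 24-month risk R is assumed). Expected events = 60 × [1 - (1 - R)^(12/104)].

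| R | Before week 12, per arm | Over 24 months, per arm | SE ratio, √(24-month/early) |
|---|---|---|---|
| 5% | 0.35 | 3 | 2.91 |
| 10% | 0.73 | 6 | 2.88 |
| 20% | 1.53 | 12 | 2.81 |

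**5. Nemours texts side by side**

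| Place | Kidney effects and fractures | Period |
|---|---|---|
| Overview, primary composite | included | none stated |
| Statistical analysis, hypothesis 2 | included | none stated for Kaplan-Meier/Cox |
| Weekly interview list | not listed | baseline to 12 weeks |
| Safety score | not covered (7 respiratory symptoms) | not stated in that item |
| Record review | listed (as renal function and bone fractures) | up to 24 months, preliminary |

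On access to control results, the Nemours text dates only disclosure to participants (8-12 weeks). Results go into the health record, the withholding described is from the portal, and study staff are unblinded. When a treating clinician can first see a control result is not stated.

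**The case against.** Several points on the other side have force.

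- **The data are labelled.** They are called exploratory at UF and preliminary at both sites. That stands. It would be wrong to say that the plan leaves this follow-up without a label. But the labels cover all 24 months and do not mark the part in which both UF arms have results.
- **UF specifies no adverse-event test between arms.** True: the analysis section prespecifies none, and one stated use is incidence. Also, by Table 1 about 39 + 20 + 5.6 = 64.6% of controls have genotypes for which the advice is that usual doses should work. That limits how far overall control incidence can move after release. It does not protect the arm contrast, which arises from the same minority of patients in both arms.
- **Week 8 or 12 at Nemours is not a clinician release date.** A reader might count 96 of 104 weeks (92.3%) as post-release there. The documents do not support that, because the dated event is disclosure to participants. With treatment stated as 8-12 weeks, the later contrast could also fade simply because the assigned period ends.
- **Record review starts at enrollment**, so it also captures fractures and kidney events in weeks 0-12, and the weekly interview suggests a 12-week study period. That stands. It cannot be inferred that the composite will rest mainly on late events, only that the plan does not say. General adverse-event monitoring might also catch such events, but it names neither as a composite source.
- **Missing text.** The Nemours text just after the overview is not in the supplied document, so a statement there cannot be excluded.

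**Conclusion.** The point holds in limited form, as something that should be changed rather than a fault in the main efficacy result.

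At UF, 88.5% of the adverse-event window follows the posting of control genotypes, and no supplied passage splits or censors there or says that both arms then have results. An unsplit 24-month difference may be biased towards no difference. The size of the bias is unknown: the range 0.71 to 0.96 in the illustration rests wholly on assumed inputs. A reader might infer that only about 11.5% of the contrast survives. That would require every control's care to follow the released result and the dosing contrast otherwise to last 24 months, and the documents establish neither. The UF 12-week RDQ and GOS comparison is complete before release and is not affected.

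At Nemours, the timing of clinician access is unclear and the dosing contrast is stated only for 8-12 weeks. Separately, and independently of genotype release, two primary composite components appear as collected items only in the preliminary review, and the time-to-event analysis has no horizon.

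**What to change.** 1. **UF reporting.** Record each control's release date in the health record. Report record-review adverse events by arm up to week 12 and after it, with the same cut-off from randomisation in both arms, and use the dates to check that no control was released earlier. Show both periods, and describe the full 24-month contrast as immediate versus delayed genotype release.
2. **Planning the next trial.** Do not use the 24-month arm difference as an undiluted dosing effect, or post-release control incidence as incidence under conventional care.
3. **Nemours access and period.** Reconcile the Study Design, Dosing and genetic results paragraphs on when clinicians and participants have access to control results and on the assigned treatment period. Split the record review at the end of that period (8-12 weeks as stated).
4. **Nemours composite.** Reconcile the overview, Study Design, adverse-event assessment, safety score and Statistical analysis texts, so that every component has a stated source and the Kaplan-Meier/Cox analysis has a stated horizon within the randomised contrast.

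The cost is wording, one date per UF control and a split table; randomisation and follow-up do not change. The drawback is precision. At UF the early period would hold about 0.4-1.5 events per arm for an assumed 24-month risk of 5-20%, with a standard error of the log hazard ratio nearly three times that of the full period. Twelve weeks is also short for fractures and kidney outcomes, which is why both periods should be shown.

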## 6. Specific Aim:

**Implement pharmacogenetic testing of the *CYP2C19* gene-PPI drug pair in the context of a comparative effectiveness genotype-supported vs. conventional treatment trial.** Given that PPI efficacy is related to PPI exposure and to metabolizer phenotype, individualizing treatment using *CYP2C19* genotype-supported dosing is expected to improve symptom control. **We hypothesize that genotype-supported treatment of GERD and dyspepsia will lead to better GERD control and improvement in the severity of dyspepsia symptoms compared to conventional treatment.** We will also survey patients and clinic staff on knowledge, attitudes, and beliefs toward pharmacogenetic testing, evaluate physician acceptance of genetic information into clinical practice, and collect preliminary data from the electronic health records on the potential impact of *CYP2C19*-supported treatment on the adverse event rate of upper respiratory infection (cold), sore throat, strep throat, bronchitis, pneumonia, ear infection, acute sinusitis (sinus infection), bone fractures, renal function, and gastrointestinal infections.

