### **Analysis Plan and Power Calculations:**

We will test the hypothesis that RMs/UMs (1 or 2 gain-of-function alleles) in the genotype-supported arm have better GERD and symptom control than RMs/UMs in the conventional treatment group because they will have their dose increased based on their genotype.

Continuous variables will be compared between the genotype-supported group and the conventional treatment group using the Student's unpaired *t*-test, and categorical variables will be compared using the chi-square or Fisher's exact test. The hypotheses will be tested using linear regression analysis to estimate the difference in the RDQ reduction in the RM/UM patients between the two arms. All analysis will be performed in SAS 9.4 (Cary, NC).

We will evaluate the percentage of the time when a dosing recommendation was made and accepted by the treating clinician, to provide practical data on the willingness of clinicians to adopt this approach. We will also collect patient- and provider-level survey data on knowledge, attitudes, and beliefs about pharmacogenetics testing, using survey tools adapted from other IRB-approved studies.

Power calculation. While there are no data in the literature on genotype associations with the efficacy endpoint we will use (symptom improvement), there are pH probe data by genotype that were generated by the Nemours investigators, that we can use, and this should be an excellent surrogate for symptom data. We have done power calculations based on two of the pH-based response phenotypes, found in Table 3. Specifically we powered based on percent time with pH < 4 (which has an effect size of 0.79) and acid clearance time (effect size of

0.45). Based on these two phenotypes, we have the following power to detect differences in efficacy between *CYP2C19\*17* carriers and non-carriers:

Based on the previous data for acid clearance time, with 180 total participants (120 from UF Health and 60 from Nemours), we have 81% power to detect a 0.49 effect size.

Based on the previous data for time with pH <4.0, with 180 participants, we have >99% power to detect a 0.79 effect size.

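### The 0.74 SD detectable effect is translated into regurgitation and heartburn differences, but the RDQ score the plan defines is a 12-item mean over three domains, and the translation does not carry over to it

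*Combined protocol and SAP*

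**What the plan says.** Under Assessment of PPI efficacy and adverse effects (section 7, Research Plan), the RDQ is described as 12 items covering heartburn, regurgitation and upper abdominal pain. One score is defined: "the RDQ mean score is calculated as the mean response to the 12 items", ranging from 1 to 6. The RDQ and the 18-symptom GOS together make up the primary outcome.

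Analysis Plan and Power Calculations tests the hypotheses by "linear regression analysis to estimate the difference in the RDQ reduction in the RM/UM patients between the two arms". It does not say whether this is the mean or a domain score, but no RDQ score other than the mean has been defined.

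The same section expects about 30 rapid or ultra-rapid metabolizers (RM/UM) per arm and states that "we will have 80% power to detect effect size of" 0.74 or more in the RDQ score, at alpha 0.05. It continues: "This effect size is equivalent to a RDQ score difference of 1.22 for regurgitation and a score difference of 0.93 for heart burn". It describes these differences as smaller than a clinically significant one, without giving that threshold, and infers that the study is well powered. No SD, detectable difference or clinically important difference is given for the 12-item mean, and none for upper abdominal pain.

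**The concern.** A standardised effect becomes a number of points only through the SD of a particular score. The figures 1.22 and 0.93 belong to two single domains, whereas the defined score averages those two with a third. A shift in one domain is divided by three in the mean, while the SD of the mean depends on all three domain SDs and on how strongly the domains correlate. The detectable difference in points, and any comparison with clinical importance, therefore has to be worked out for the mean itself.

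At stake is what the sample-size justification supports. A reader would take it that a 1.22-point regurgitation benefit, or a 0.93-point heartburn benefit, would be found with 80% power by the planned test. If that test uses the 12-item mean, this has not been shown, and for a benefit confined to one of those domains it is not so. The gap also matters because the specific aim has two parts, "better GERD control and improvement in the severity of dyspepsia symptoms compared to conventional treatment", and the power statement gives no figure for the one RDQ domain closest to dyspepsia.

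**Working it through.** **Inputs from the plan:** 30 RM/UM patients per arm; alpha 0.05; effect 0.74 SD; differences of 1.22 (regurgitation) and 0.93 (heartburn); mean of 12 items over three domains.

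**Assumed, because the plan does not give them:** two-sided test; four items per domain, so each domain has weight 1/3; a common correlation ρ between domains, from 0 to 1; upper-abdominal-pain SD s_A between the two implied SDs; implied SDs taken to be those of the quantity tested.

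**1. The plan's own figure.** Noncentrality 0.74 × √(30/2) = 2.87 on 58 degrees of freedom gives 80.5% power (81.8% by the normal approximation). The smallest d detectable with 80% power is 0.736. The stated 80% reproduces for any score whose true effect is 0.74 of its own SD.

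**2. Implied domain SDs.** Regurgitation: s_R = 1.22/0.74 = 1.65. Heartburn: s_H = 0.93/0.74 = 1.26. Hence s_A is taken from 1.26 to 1.65.

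**3. SD of the 12-item mean.**

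SD = √[s_R² + s_H² + s_A² + 2ρ(s_R·s_H + s_R·s_A + s_H·s_A)] / 3

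- Lowest (ρ = 0, s_A = 1.26): √(2.72 + 1.58 + 1.58)/3 = 0.81, so 0.74 SD = 0.60 points.
- Highest (ρ = 1, s_A = 1.65): (1.65 + 1.26 + 1.65)/3 = 1.52, so 0.74 SD = 1.12 points.

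**4. How far the mean moves.**

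- Regurgitation only: 1.22/3 = 0.41.
- Heartburn only: 0.93/3 = 0.31.
- Both, with no pain effect: (1.22 + 0.93)/3 = 0.717.
- All three by 0.74 of their own SD: (1.22 + 0.93 + 0.74·s_A)/3 = 1.03 to 1.12.

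**5. Power on the mean**, two-sided t-test, 30 per arm, d = movement/SD. Ranges run over s_A from 1.26 to 1.65.

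| ρ | 0.74 SD in points | Regurgitation only | Heartburn only | Both, no pain effect | All three |
|---|---|---|---|---|---|
| 0 | 0.60–0.65 | 42–48% | 27–31% | 87–92% | >99% |
| 0.3 | 0.75–0.82 | 29–33% | 19–21% | 69–77% | 97% |
| 0.5 | 0.84–0.92 | 24–28% | 16–18% | 59–67% | 93% |
| 0.7 | 0.92–1.01 | 21–24% | 14–16% | 52–59% | 88% |
| 1.0 | 1.03–1.12 | 18–20% | 12–14% | 44–50% | 80.5% |

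With both domains moving and no pain effect, the standardised effect on the mean falls below 0.74 once ρ exceeds about 0.10 (s_A = 1.65) to 0.22 (s_A = 1.26).

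**6. A patient with upper abdominal pain only.** Eight items stay at 1 and four can reach 6, so the mean lies between 1.00 and (4×6 + 8×1)/12 = 2.67. The largest possible fall is 1.67 points.

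**The case against.** The strongest reply is that the power claim is made for a standardised effect in the RDQ score and is correct as such; only its translation into points is incomplete. That stands: the 80% is not wrong.

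A reader might go further and infer that the 12-item mean has less than 80% power for the benefit the trial hopes to see. The documents do not support this as a general statement. It needs an effect confined to one domain, or no effect on upper abdominal pain together with a correlation above about 0.10–0.22. The aim itself expects dyspepsia to improve, and if all three domains shift by 0.74 SD, averaging keeps or raises the standardised effect. Neither the correlation nor the third SD is given, so no single power figure can be asserted.

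A reader might also infer that the mean can barely move in patients with dyspepsia only. Upper abdominal pain is one of the three domains, so its change is diluted to one third rather than lost. The share of such patients is not stated, and the GOS, also part of the primary outcome, covers wider symptoms.

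Finally, the analysis section says only RDQ reduction, so domain scores may have been intended. That is possible, but no domain score is defined as an endpoint, and the tested score would then still need to be named.

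**Conclusion.** The point holds as a mismatch between the score defined and the scores used to justify the sample size. The differences of 1.22 and 0.93 are not the detectable difference on the 12-item mean, which is about 0.60–1.12 points under the stated assumptions. The claims about clinical significance and adequate power, which rest on those two figures, are therefore not established for the defined score.

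The size depends on where benefit falls. For a benefit confined to regurgitation or to heartburn, power on the mean is well under 80% at every correlation from 0 to 1. For both together without a pain effect, the result turns on the unknown correlation. For an equal standardised shift in all three domains there is no loss.

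These figures take the plan's 30 per arm at face value. Whether the Nemours children contribute RDQ data is a separate matter: the questionnaires listed in the Nemours part do not include it.

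**What to change.** In Analysis Plan and Power Calculations:

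- State that the tested RDQ score is the 12-item mean as section 7 defines it.
- Delete the 1.22/0.93 equivalence and the inference of adequate power drawn from it.
- Give the SD of the tested score with its source, the resulting detectable difference in points, and the clinically important difference for that same score with its source. If no SD for the mean is available, show the range with the assumed correlation and domain SDs.
- Report the heartburn, regurgitation and upper-abdominal-pain domains and the GOS as supportive analyses of the RDQ test, and reconcile that role with section 7, which names the GOS in the primary outcome.

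Replacing the mean with an eight-item heartburn and regurgitation score is optional. It would gain power if pain does not respond, but it would give no credit for a pain response, and the plan describes only the RDQ mean score as validated.

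The cost is a few sentences in the analysis plan. All items are already collected, and neither the sample size nor the visit schedule changes.
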